### ***2.1.3 Randomized Period Post-Treatment Follow-Up***

Patients who do not enter the OLE period will go straight to the 13-week post-treatment follow-up period. This period consists of 7 visits, as outlined in the Schedule of Procedures in Appendix A of the protocol.

### ***2.1.4 OLE Period***

After completion of the 52-week randomized treatment period patients will enter the OLE period and will receive volanesorsen for an additional 52 weeks. Assessments and study visits will be generally similar to the randomized treatment period as outlined in the Schedule of Procedures in Protocol Appendix A, with the inclusion of weekly platelet monitoring.

Following 52 weeks of treatment in the Open-Label Extension Period, patients will have the option of continuing dosing for up to an additional 52 weeks. The schedule of procedures will follow the same schedule as the first year of OLE.

### ***2.1.5 OLE Post-Treatment Period***

Following the Week 52 visit of the Open-Label Extension Period, patients will have the option of continuing dosing for up to an additional 52 weeks (second OLE period). Patients who do not enter this option for additional dosing in the OLE period will go straight to the 13-week OLE post-treatment period after completion of the first 52 weeks or after discontinuing treatment during the first 52 weeks of OLE. This period consists of 7 visits, as outlined in the Schedule of Procedures in Protocol Appendix A.

For patients who continue to receive investigational treatment for the second OLE period, the 13-week OLE post-treatment period will follow completion of the Week 156 visit or after early treatment discontinuation.

## ***2.2 Randomization and Treatment Allocation***

Patients will be randomized after all screening and qualification assessments have been completed and after the Investigator has verified that they are eligible per criteria in the protocol sections 5.1 and 5.2. No patient may begin treatment prior to randomization and assignment of a unique patient identification number.

Using an Interactive Voice/Web-Response System (IxRS), eligible patients will be randomized 1:1 to receive volanesorsen or placebo.

Patients will be stratified by assignment into 1 of 3 groups based on FPL phenotype, genetic variants and family history of PL. (Minor criteria refers to protocol section 5.1 inclusion criteria)

### **FPL Groups for Stratification**

1. Group 1 will consist of patients with the FPL phenotype and genetic variants of FPL.
2. Group 2 will consist of patients with the FPL phenotype, but lacking a genetic variant, and having a confirmed family history of FPL or abnormal and similar fat distribution, plus 1 minor criterion.
3. Group 3 will consist of those with the FPL phenotype, but without either a genetic variant or family history, plus 2 minor criteria and a  $BMI < 35 \text{ kg/m}^2$ .

Genetic analysis reports include characterization of variants into 5 classifications: benign, likely benign, variant of unknown significance, likely pathogenic or pathogenic.

#### For stratification purposes:

Positive on genetic testing: Documentation of pathogenic or likely pathogenic genes associated with familial partial lipodystrophy will be considered positive for genetic analysis if these changes are likely to represent the underlying cause of the subject's phenotype. This should be documented in a written report.

Negative on genetic testing: When sequencing analysis of the partial lipodystrophy panel for variants determines that no pathogenic or likely pathogenic variant were identified or is a variant of unknown significance, this will be considered as evidence for negative for genetics. Negative on genetics will also be considered for those subjects for whom the genetic analysis results are unlikely, unknown, or untested.

Positive family history of FPL or family history of abnormal and similar fat distribution includes immediate family / first degree relatives (father, mother, brother, sister, daughter, son), as well as second degree relatives (grandparents, aunts and uncles, nieces and nephews, and grandchildren).

A permuted block schedule will be used. The Sponsor Quality Assurance department or designee will hold a copy of the randomization lists generated by the IxRS vendor.

Patients who withdraw from the study will not be replaced.

### **2.3     *Conduct***

The study will be conducted in accordance with current Good Clinical Practice (GCP) and International Conference on Harmonization (ICH) guidelines, the World Medical Association Declaration of Helsinki guidelines, the Food and Drug Agency (FDA) Code of Federal Regulations, and all other local regulatory requirements.

## **2.4 Data Monitoring**

### **2.4.1 Safety Data Monitoring**

The Sponsor (or designee) is responsible for processing all reported adverse events (AEs). Processing of serious adverse events (SAEs) is delegated to a CRO although the Sponsor remains accountable for this activity and process. AEs and SAEs are reviewed according to standard operating procedures. The Sponsor medical monitor will review all AEs and SAEs on an ongoing basis throughout the study. The Sponsor (or designee) will prepare and submit safety reports to the health authorities worldwide in accordance with local requirements. If it becomes necessary to communicate new safety information, the Sponsor (or designee) will also prepare a safety notification letter and transmit it to all applicable study sites.

### **2.4.2 Data Monitoring Board**

An independent Data and Safety Monitoring Board (DSMB) will be assembled to review safety, tolerability and efficacy (as needed) data collected on volanesorsen during this study. Based on its ongoing assessment of the safety and tolerability of volanesorsen, the DSMB will provide recommendations to the Sponsor for modifying, stopping or continuing the study as planned. Details on the safety assessments, frequency of review, meeting schedules and controlled access to unblinded data are outlined in the DSMB Charter.

In order to ensure maintenance of the study blind, lipid panel results, including apoC-III, will not be available to the Sponsor, monitors, Investigators, Study Center personnel, or the patients, except for the procedure related to safety monitoring for LDL-C elevations as specified in protocol section 8.5.6.

For the purpose of pre-programming and data cleaning, Parexel unblinded programming team (the CRO performing the statistical analysis) and an independent data manager at [REDACTED] Laboratories will receive post-baseline lipid panel results.

[Appendix A](#) lists what data will be included in the DSMB.

## **2.5 Data Management**

### **2.5.1 Case Report Form (CRF) Data**

Bioclinica® is responsible for creating the Electronic Data Capture (EDC) data entry screens, database and edit checks using definitions developed by the Sponsor (or designee). The Sponsor (or designee) is responsible for the review, data management querying, and locking of the database.

Data are single-entered into the EDC system by the Investigator site staff. Programmed edit checks (computer logic that checks the validity of the data entered and also prompts for missing data that is expected to be entered) are run and automatic queries are generated. The Sponsor performs blinded review of all data for accuracy and validity; generating additional queries in the EDC system, when necessary. The data is corrected or an explanation concerning the query is provided in the EDC system. After all data is entered, reviewed, source data verified, and after all queries are resolved, the database will be locked.

### **2.5.2 *Laboratory Data***

The Sponsor is responsible for the format of the laboratory electronic data transfers and the transfer schedule. The Sponsor (or designee) is responsible for the review of the clinical laboratory data. Central lab data is not stored in the EDC system. Investigator sites have access to this data via printed lab reports sent directly from the laboratory. MRL manages the Central lab data.

### **2.5.3 *Pharmacokinetics (PK) and Anti-drug Antibody (ADA) Data***

The Sponsor is responsible for the management and review of the PK and IM data. This process involves reviewing the patient and visit identifiers with the clinical data collected in the EDC system. The PK and IM data are not stored in the EDC system.

### **2.5.4 *Other Data***

██████████ Central Lab manages MRI/ECHO/██████████. Both data will also not be stored in the EDC system but will be transferred to Ionis Pharmaceuticals, Inc. as external data.

### **2.5.5 *Adverse Events Adjudication***

SOCAR is the vendor that manages the adjudication process. All SAEs that occur during the study that are consistent with MACE will be adjudicated by a blinded, independent committee as outlined in the MACE Adjudication Charter. In addition, this committee will also adjudicate the data for episodes of MACE over the last 3 years prior to randomization, collected by review of each patient's medical chart. All AEs and SAEs that occur during the study that are consistent with an event of acute pancreatitis will be adjudicated by a blinded, independent committee according to the Atlanta classification of acute pancreatitis (Banks et al. 2013) and as outlined in the Pancreatitis Adjudication Charter.

The adjudication data will be transferred electronically using EXCEL file from SOCAR to Ionis Pharmaceuticals, Inc.

## **3 ANALYSIS PLAN**

### **3.1 *Statistical Design Summary***

This is a multi-center, randomized, double blind, placebo-controlled study with an open-label extension comprised of study periods outlined in Section 1.1.

The primary efficacy measurement is fasting triglyceride which will be collected at baseline and all post-baseline visits. The primary analysis model will be a parametric analysis model for percent change in triglyceride from Baseline to Randomized Treatment Period Month 3 by treatment group. As study treatment is discontinued before completing the protocol specified treatment period, missing data imputation and various sensitivity analyses defined by protocol will not be conducted.

The primary endpoint for the study will be evaluated after the last patient has completed the Week 52/early termination (ET) visit and will be based on the percent change from Baseline in fasting TG at the primary analysis time point (Month 3). The Study Team will be unblinded after the last patient's Week 52/ET visit is completed and database is locked.

### **3.2 General Overview of Analyses**

#### **3.2.1 Statistical Methods**

All eCRF(Electronic Case Report Form) data, lab data transfers, as well as any outcomes derived from the data, will be provided in the patient data listings. Patient data listings will be presented for all patients randomized into the study. Descriptive summary statistics including n, mean, median, standard error, standard deviation, interquartile range (25th percentile, 75th percentile), range (minimum, maximum) for continuous variables, and counts and percentages for categorical variables will be used to summarize most data. Where appropriate, p-values will be reported. All statistical tests will be conducted using 2-sided tests with 5% Type 1 error rates unless otherwise stated.

Summary of primary efficacy endpoint will only include the on-treatment assessment. On-treatment assessment is defined as assessment since first dose date, up to 28 days after last dose of study medication. Assessment beyond last dose of study medication + 28 days will be excluded from efficacy summary. Lipid, hepatic fat fraction, and HbA1c assessments will be summarized by analysis visit according to the visit window defined in [Appendix B](#). Other assessments will be summarized by nominal visit as collected in CRF.

Lipid (triglyceride and non-triglyceride), hepatic fat fraction, and HbA1c data will be mapped to analysis visit as specified in [Appendix B](#). Assessments collected during randomized treatment period, will have analysis visit assigned according to the days relative to first dose date of randomized treatment period. Assessments collected during OLE period will have analysis visit assigned according to the days relative to first dose date of OLE period. The intent of these analysis visit windows is not to align with those prescribed for visit scheduling in the clinical study protocol but, rather, based on the protocol-defined target study day, to delineate mutually exclusive windows so that all efficacy assessments proximal to a particular study week can be integrated to best represent the patient's status during that period of the study. If a patient discontinued early from the treatment period but attended applicable landmark visits at Weeks 12, 13, 25, and etc. to collect lipid assessments, then those assessments collected at ET visit and during post-treatment follow-up period should be mapped to analysis visits as well, excluding assessment beyond 28 days after last dose of study medication. For the hepatic fat fraction and HbA1c data, data collected within the analysis visit window defined in [Appendix B](#) will be used. If there are multiple assessments within a visit window, only scheduled visit will be used, and the average will be used if there are multiple scheduled assessments, or the worst will be used if categorical result is collected in multiple scheduled assessments. If the assessments are all unscheduled, the visit nearest the scheduled date will be used, unless 2 visits are equally near, in which case the average will be used, or the worst will be used if categorical result is collected.

For efficacy data, local lab data will not be used unless central lab assessments are not available at certain visit. When calculating the baseline and analysis endpoints, only if the data from central lab is missing, then the local lab data will be utilized.

Safety assessments will be summarized by the nominal visit as collected in CRF. Multiple results with the same nominal visit will be averaged.

For safety lab, unscheduled assessment (both central lab and local lab) will not be included in the by-visit summaries, except for platelet analysis. Unscheduled results from the central lab will be used in the determination of baseline, laboratory abnormality summaries, shift from Baseline to worst post-baseline, and platelets reduction analyses. Local lab will be used in the determination of laboratory

abnormality summaries, shift from Baseline to worst post-baseline, and platelets reduction analyses, but not in baseline determination. For platelet, when central lab is not available at baseline, local lab result will be used in baseline determination.

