### ***10.6.3 Efficacy Analysis (Primary and Secondary)***

The primary efficacy analysis will be the comparison of percent change from Baseline to the primary analysis time point in fasting TG between ISIS 304801 300 mg once-weekly group and placebo group in the FAS. The data will be analyzed using an analysis of covariance (ANCOVA) model with the randomization stratification factor (diagnosis of disease with or without genetics and family history) and Baseline TG as covariates. In the ANCOVA model, TG will be log-transformed. Patients with a missing primary endpoint will have TG value multiply imputed using an imputation model that contains the following variables: baseline TG, TG values at post-baseline visits and the stratification factor, and the multiple imputation will be stratified by treatment ([Schafer 1997](#); [Schafer 1999](#)). Any patient who discontinues early from the Treatment Period will be strongly encouraged to attend applicable landmark visits including Weeks 12 and 13 during which TG values will be collected and used in the primary analysis.

The primary efficacy analysis will take place after the last patient has completed the Week 52/ET visit and the database has been locked, and will be based on the percent change from Baseline in fasting TG at the primary analysis time point (end of Month 3).

A few sensitivity analyses using controlled imputations (pattern mixture models (PMM) with ANCOVA) will be conducted to assess the robustness of the primary analysis results on both the FAS and PPS. With this approach, missing not at random (MNAR) is assumed and the mean

function for the missing data from patients who discontinue the study is pre-specified in ways that assess the robustness of the MAR assumption. The mean function parameterization will be completed using the following approaches:

- Patients treated with volanesorsen who discontinue the study due to lack of efficacy or Adverse Events or other types of treatment failure will have missing post-treatment discontinuation TG values multiply imputed using estimates from the placebo patients. Specifically, the copy increment from reference (CIR) approaches will be used. Otherwise, non-informative missing data will be imputed using MI method as the same as the primary analysis

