- All patients treated with volanesorsen who discontinue the study will have missing post-treatment discontinuation TG values multiply imputed using estimates from the placebo patients. Specifically, the copy increment from reference (CIR) approaches will be used
- Patients treated with volanesorsen who discontinue the study will have missing post-discontinuation TG values multiply imputed based on baseline TG and the imputation model for the placebo

The additional sensitivity analyses will be conducted for the primary efficacy analysis, and details of the analyses will be specified in the SAP:

- The primary analysis will be repeated in the PPS
- The primary analysis will be repeated in the subset of FAS who have a non-missing primary endpoint
- The following analyses will be conducted on both the FAS and PPS:
  - The primary analysis will be repeated to compare the percent change from Baseline to average of Weeks 8 (Day 50), 12 (Day 78) and 13 (Day 85) between treatment groups. Missing data will not be imputed
  - The primary efficacy endpoint will be analyzed using Wilcoxon rank-sum test for sensitivity analysis, and the treatment effect will be estimated using Hodges-Lehmann estimator
  - For the responder analysis described above, all patients with a missing primary endpoint will be considered as non-responders
  - The primary efficacy endpoint will also be analyzed using the nonparametric Wei-Johnson method

Secondary [REDACTED] efficacy analyses will be conducted in both the FAS and PPS, and described fully in the SAP:

- Change from Baseline in hepatic fat fraction (%) as assessed by MRI will be compared between ISIS 304801 300 mg qw and placebo groups using an ANCOVA model with baseline and the stratification factor as covariates

- Change from Baseline in HbA1c will be compared between ISIS 304801 300 mg once-weekly and placebo group using an ANCOVA model with baseline and the stratification factor as covariates

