### **3.2.3 Baseline and Endpoint Definition**

**The baseline for fasting lipid measurements** is defined as the average of Day 1 pre-dose assessment and the last non-missing measurement prior to Day 1 pre-dose assessment. If 1 of the 2 measurements is missing, then the other measurement will be assigned as the baseline value. If both are missing, then the baseline will be set as missing and the patient will be excluded from the FAS. Note that if on Day 1, there are multiple pre-dose assessments, then the last assessment with non-missing value will be used as the Day 1 pre-dose assessment.

**The baseline for other measurements** is defined as the last non-missing assessment prior to the first dose of Study Drug with the exception that platelet baseline is defined as the average of all assessments prior to the first dose of Study Drug.

Randomized Treatment Period and Open-Label Extension Period refer to one baseline, which is based on the pre-dose assessment of Day 1 in Randomized Treatment Period.

Efficacy by visit summary will include following time point, when data available. Both visit week and month will be presented.

**Randomized Treatment Period Month 3 analysis time point** is at the end of Randomized Treatment Period Month 3. For fasting lipid measurements, value at Month 3 is defined as the average of Week 12 (Day 78) and Week 13 (Day 85) fasting lipid measurements. If one visit is missing, then the other visit will be used. If both visits are missing, then the value will be set as missing

**Randomized Treatment Period Month 6 analysis time point** is at the end of Randomized Treatment Period Month 6. For fasting lipid assessments, value at Month 6 is defined as the average of Week 25 (Day 169) and Week 26 (Day 176) fasting assessments. If one visit is missing, then the other visit will be used. If both visits are missing, then value will be set as missing. .

**Randomized Treatment Period Month 12 analysis time point** is at the end of Randomized Treatment Period Month 12. For fasting lipid assessments, value at Month 12 is defined as the average of Week 50 (Day 344) and Week 52 (Day 358) fasting assessments. If one visit is missing, then the other visit will be used. If both visits are missing, then the value will be set as missing. .

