### **3.3.5 Incomplete or Missing Data**

Patients with a missing primary endpoint will be excluded from primary efficacy analysis.

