### **3.8 Changes in the Planned Analysis**

Study treatment is discontinued before completing the protocol specified treatment period. The following protocol specified analysis will not be conducted at the final analysis.

1. Protocol section 10.3 “Per Protocol Set (PPS)”, in final analysis, Per Protocol Set will not be classified. All analysis endpoint will not be assessed in PPS.
2. Protocol section 10.6.3 primary efficacy analysis, patient with missing primary endpoint will be excluded from primary efficacy analysis (ANCOVA). Protocol specified imputation method and sensitivity analysis to assess the robustness of the primary analysis results will not be conducted. For secondary efficacy analysis (patients who achieve a  $\geq 40\%$  reduction in fasting triglyceride from Baseline and  $\geq 30\%$  reduction of hepatic fat fraction percent from baseline at Month 6), protocol specified statistical comparison will not be conducted, only descriptive summary will be provided. The change from baseline in fasting triglycerides, hepatic fat fraction, and HbA1c will be assessed using ANCOVA model with derived FPL based off of genetic confirmation as a stratification factor. A subset analysis will look at the change from baseline in fasting triglycerides, hepatic fat fraction, and HbA1c by gene mutation of LMNA + PPARG and no mutation. The ANOCOVA model used for this analysis will include an interaction term between treatment and FPL group
3. Protocol section 10.1.2 states that Disease burden score is one of secondary efficacy endpoint. However this patient-reported outcome is not collected in the study. Disease burden score will not be summarized.

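### The SAP turns the primary triglyceride analysis into an on-treatment, observed-case analysis, contrary to the protocol, and does not list its 28-day rule as a change

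*SAP*

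**What the plan says.** Protocol 10.6.3 asks patients who stop early to return for landmark visits, including Weeks 12 and 13, "during which TG values will be collected and used in the primary analysis". It sets no limit on time since last dose. Endpoints still missing are multiply imputed, stratified by treatment. Controlled-imputation analyses that borrow from placebo are planned to test the result. An observed-case analysis appears only among the further sensitivity analyses: "The primary analysis will be repeated in the subset of FAS who have a non-missing primary endpoint".

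SAP 3.2.1 restricts the primary endpoint to on-treatment values: "Assessment beyond last dose of study medication + 28 days will be excluded from efficacy summary". For landmark visits attended after early discontinuation, lipids are mapped to analysis visits "excluding assessment beyond 28 days after last dose of study medication". SAP 3.2.3 builds Month 3 from the Week 12 and Week 13 visits ("If one visit is missing, then the other visit will be used") and sets it to missing when neither is available. SAP 3.3.5 then states: "Patients with a missing primary endpoint will be excluded from primary efficacy analysis".

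SAP 3.1 adds that "missing data imputation and various sensitivity analyses defined by protocol will not be conducted", and SAP 3.8 repeats it: "Protocol specified imputation method and sensitivity analysis to assess the robustness of the primary analysis results will not be conducted". SAP 3.8 also drops the Per Protocol Set. Neither SAP 3.8 nor the SAP's Summary of Changes mentions the 28-day rule.

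**The concern.** The two documents give opposite instructions for the same observation. A fasting triglyceride drawn at Week 12 from a patient who stopped at Week 6 enters the protocol's primary analysis. Under the SAP it is treated as missing and the patient leaves the ANCOVA.

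Whether a randomised, dosed patient counts then depends on when dosing stopped, which treatment can influence. Membership of the Full Analysis Set is unchanged, and SAP 3.2.2 still presents that set as intent-to-treat, but the primary model is no longer fitted to all of it. The analyses that could show the size and direction of any resulting bias are cancelled in the same document. A reader relying on SAP 3.8 would see that imputation was dropped, but not that observed values are left out.

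SAP 3.1 and 3.8 cite the early end of study treatment as the reason for dropping imputation, sensitivity analyses and the Per Protocol Set. No reason is given for the 28-day rule.

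**Working it through.** **Does the rule reach the ANCOVA?** The sentence in SAP 3.2.1 about the efficacy summary could be read as descriptive only, and SAP 3.3.2 does not repeat it. The mapping paragraph in SAP 3.2.1 settles the matter. Values beyond 28 days are not assigned to the Week 12 or Week 13 analysis visits, and SAP 3.2.3 forms the modelled Month 3 value from those visits.

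**Who loses the endpoint.** A value is kept if assessment day ≤ last dose day + 28. Target days are 78 and 85 (SAP 3.2.3).

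| Last dose | + 28 | Week 12 (Day 78) | Week 13 (Day 85) |
|---|---|---|---|
| Day 43 (7th weekly dose) | 71 | lost | lost |
| Day 50 | 78 | kept | lost |
| Day 57 | 85 | kept | kept |

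- Nominal days: a last dose before Day 50 (78 - 28) removes the patient. A last dose on Days 50 to 56 loses Week 13 only, and one value suffices.
- Protocol visit window of ±2 days: the earliest Week 12 draw is Day 76, so a last dose by Day 47 loses both.
- SAP Appendix B window (Week 12 = Days 65 to 82): loss is certain only for a last dose before Day 37 (65 - 28).
- The mapping rule covers all lipid visits, so the Month 6 and Month 12 repeats of the ANCOVA are affected too. At nominal days the cut-offs are Day 141 (169 - 28) and Day 316 (344 - 28).

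**Planning inputs** (Protocol 10.2, SAP 3.3.3): means -50% and -10%, SD 40, 20 per arm, alpha 0.05 (two-sided per Protocol 10.6). The plan states about 80% power. These inputs give 88.5% (normal approximation) or 86.9% (t), so the stated figure is not reproduced. That is a separate, conservative discrepancy and does not bear on this point. The unadjusted standard error of the difference is 40 × √(2/20) = 12.65 points.

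**Size of bias.** Let d and q be the shares deleted on active and placebo. Let L be the response lost by deleted active patients and R the rise in deleted placebo patients, both in points from the retained arm mean. The SAP analysis estimates -10 - (-50) = 40. Using everyone, the difference is (-10 + qR) - (-50 + dL) = 40 - dL + qR. So overstatement = dL - qR.

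The documents give no stopping rate by arm and no off-drug triglyceride level. The values of d, q, L and R below are assumptions.

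| Case | d | L | q | R | Overstatement (points) |
|---|---|---|---|---|---|
| Full loss, back to -10% | 5%, 10%, 20% | 40 | 0 | – | 2, 4, 8 |
| Half the effect lost | 5%, 10%, 20% | 20 | 0 | – | 1, 2, 4 |
| Response persists | any | 0 | 0 | – | 0 |
| Placebo stoppers at +20% | 0 | – | 10% | 30 | -3 |
| Both arms | 5% | 20 | 5% | 30 | -0.5 |

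The full-loss figures are 2/12.65 = 0.16, 4/12.65 = 0.32 and 8/12.65 = 0.63 standard errors.

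The only related count is in Protocol 2.3.4: 6 of 182 patients in blinded trials, about 110 of them on drug, had dosing interrupted or stopped for platelets. If all 6 were on drug and all were deleted, d = 6/110 = 5.45%, giving 2.2 points (full loss) or 1.1 (half loss).

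**The case against.** The sponsor could argue that the harm is unproven and most of the change is disclosed. Every bias figure rests on assumed shares. Protocol 2.3.4 describes effects that outlast dosing, so triglycerides may still be suppressed after 28 days. Even 20% deletion with full loss leaves 32 points, about 2.5 standard errors. SAP 3.8 openly lists the loss of imputation and sensitivity analyses, and the 28-day rule is written out in SAP 3.2.1. The excluded values remain in the patient listings, and SAP 3.2.4 tabulates discontinuations with reasons by arm.

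Much of this stands. No change of conclusion is shown. The 6 of 182 count is a weak proxy: it comes from other trials, is blinded, has no timing, and includes interruptions, whereas a patient who resumes before Month 3 may lose nothing. L = 40 is a ceiling only under the planned means; Protocol Table 1 reports mean falls of 64% to 72%, so full loss could be larger. Loss of the treatment-stratified imputation is not itself shown to favour the drug. That imputation fills gaps from the same arm, so it would not correct for lost response; only the observed values or a placebo-based analysis would.

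None of it removes the conflict. Values in a listing do not enter the estimate, and counts of discontinuation do not show what the estimate would have been with those values included. If response does persist, including them costs the sponsor nothing.

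**Conclusion.** The point holds and should be corrected. The SAP's primary analysis contradicts Protocol 10.6.3. It is a stricter, on-treatment form of what the protocol planned only as a sensitivity analysis. The rule that excludes observed Month 3 values is neither justified nor listed as a change.

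The direction of bias is conditional. It favours the drug if active-arm stoppers have lost response by Month 3, is nil if nobody stops early or response persists, and reverses if placebo stoppers with rising values are removed. Under the planned means and the assumed shares it ranges from 3 points of understatement to 8 points of overstatement, against a standard error of 12.6. At 20 per arm, one deleted patient is 5% of an arm. The case for correction rests on selection after randomisation with no planned analysis able to reveal its effect, not on a demonstrated large bias.

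**What to change.** - In the primary ANCOVA, use every observed Week 12/13 fasting triglyceride regardless of time since last dose, as Protocol 10.6.3 states.
- Restore the protocol's treatment-stratified multiple imputation for endpoints still missing.
- Keep at least one placebo-based sensitivity analysis (copy increment from reference).
- Report the 28-day, observed-case analysis as supportive.
- Tabulate by arm how many patients and values the 28-day rule removes.
- List the rule in SAP 3.8 with its reason.

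The cost is SAP wording and modest programming. Protocol 8.8.1 only encourages landmark attendance, so the number of values recovered is unknown and may be small. The effect estimate may become smaller.
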